2.5.4 Unscheduled visits

Unscheduled MRI scans and SDMT will be assigned to the appropriate analysis window (defined in [Table 4](#) and [Table 5, Section 2.5.3](#)). Otherwise, only scheduled visit efficacy measurements will be used for by visit analysis to exclude the temporary fluctuations in the clinical status that may occur with a relapse.

Laboratory and vital sign data from unscheduled visits will be used in PCSA analysis. The unscheduled visits will also be assigned to the appropriate analysis time window (defined in [Table 6](#) and [Table 7, Section 2.5.3](#)) for the summary of change from baseline by visit. The

one closest to the targeted visit date will be used in the presence of multiple measurements within the same time window.

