### **8.1 EFFICACY**

In order to assure proper evaluation of the efficacy, at each study center the staff will consist of a minimum of 2 neurologists. One neurologist will be the treating neurologist and one will be the examining neurologist for a given subject throughout the study. One of the neurologists may be the Principal Investigator. This delineation assures that AEs or other health issues for any patient do not influence the neurological assessment. In case an assessment (eg, EDSS/FS, MRI) cannot be performed during to a regional or national emergency, the patients will be asked to stay at home, and study visits that are scheduled during this outbreak may be replaced by phone calls, and study assessments that require an on-site visit may be performed at the next scheduled visit or as unscheduled evaluation ([Section 17.7](#)).

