**Table 6 – Overview of study assessments**

Assessments	V19 / W96 EOT	V11 / W48 V27 / W144	V7/ W24* V15 /W72 V23/W120 V31/W168	V9W36* V13 / W60 V17 / W84 V21/ W108 V25/ W132 V29/ W156 V33/ W180	V6 / W20 V8 / W30 V10 / W42 VV12 / W54 V14 / W66	(Visits timeframe: +/-7DAYS)
	On site visit if possible	On site visit if possible	On site visit if possible	On site visit if possible	On site visit if possible	
Efficacy						
EDSS/FS	X	X	X			If the visit at site not possible at planned visit date this assessment to be done at next scheduled visit as unscheduled evaluation
SDMT	X	X	X			If the visit at site not possible at planned visit date this assessment to be done at next scheduled visit as unscheduled evaluation
Cognitive tests	X					If the visit at site not possible at planned visit date this assessment to be done at next scheduled visit as unscheduled evaluation
Brain MRI	X	X				If the visit at site not possible at planned visit date this assessment to be done at next scheduled visit as unscheduled evaluation
Safety						
Vital signs (In case of DTP*, patient/parent to provide the weight per self-evaluation)	X	X	X	X		If the visit at site not possible at planned visit date this assessment to be done at next scheduled visit or as unscheduled evaluation
Physical examination	X	X	X			If the visit at site not possible at planned visit date this assessment to be done at next scheduled visit if expected or as unscheduled evaluation
ECG 12-leads	X (only EOT)					
Tanner	X	X	X			If the visit at site not possible at planned visit date this assessment to be done at next scheduled visit if expected or as unscheduled evaluation
Clinical routine laboratories	X	X	X	X		If the visit at site not possible at planned visit date this assessment to be done at next scheduled visit if expected or as unscheduled evaluation
Clinical safety laboratories					X	If the visit at site not possible at planned visit date this assessment to be done as unscheduled evaluation
Treatments						

Concomitant medications	X	X	X	X	X	If the visit at site not possible at planned visit date to be checked by phone call and at the subsequent visit at site
Dispense study drugs/IVRS call	X	X	X	X		DTP* in case patient cannot come at site
Accountability / compliance	X	X	X	X		If the visit at site not possible at planned visit date compliance to be checked by phone call and subsequent visit at site

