2.4.4.2.4 EDSS

EDSS score and the change from baseline in EDSS score in the double-blind period will be summarized with descriptive statistics at each visit by treatment group.

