2.4.4.2.5 Cognitive outcome

The change from baseline in Cognitive Battery Tests and SDMT will be summarized descriptively. Box plot will be provided as well.

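### COVID-delayed EDSS and Cognitive Battery results recorded as unscheduled fall out of the open-label by-visit summaries under SAP 2.5.4, and the battery has no other planned analysis

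*SAP*

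**What the plan says.** Protocol Appendix H, Table 6 (global memo of 24 March 2020) gives the same instruction for EDSS/FS, SDMT, cognitive tests and brain MRI: "If the visit at site not possible at planned visit date this assessment to be done at next scheduled visit as unscheduled evaluation". Table 5 (China memo of 21 February 2020) has the same rule. Protocol section 8.1 is looser: "study assessments that require an on-site visit may be performed at the next scheduled visit or as unscheduled evaluation".

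SAP 2.5.4 treats these measures differently. For two of them, "Unscheduled MRI scans and SDMT will be assigned to the appropriate analysis window". For all others the rule is: "Otherwise, only scheduled visit efficacy measurements will be used for by visit analysis". The stated purpose is to keep out short-lived changes that a relapse may cause.

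The affected summaries are in SAP 2.4.4.2.4, where EDSS "will be summarized with descriptive statistics at each visit by treatment group", and SAP 2.4.4.2.5: "The change from baseline in Cognitive Battery Tests and SDMT will be summarized descriptively". SAP Table 2 schedules the open-label battery at Week 96 and Week 192/EOT only. SAP Table 5 gives open-label windows for SDMT and MRI, and none for EDSS or the battery.

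**The concern.** A site that follows the protocol's table produces a record labelled unscheduled. The SAP then uses that label to decide what enters a by-visit summary. The only reason given for the exclusion is that clinical status may fluctuate around a relapse. That does not describe an assessment postponed because the patient could not travel.

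Version 2 of the SAP was revised for COVID-19. Its change table lists censoring rules and the open-label EOT window, and the text rescues delayed MRI (2.4.4.2.3) and delayed EDSS for progression (2.4.4.3.2). Neither repairs the by-visit EDSS summary or the battery. Protocol 17.7 leaves it to the SAP to set out the methods needed for data missing because of the emergency.

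Cognitive function is part of a secondary objective and the battery is a listed secondary outcome. At stake is whether valid results reach the only summary planned for them.

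**Working it through.** No figure in the plan needs reproducing. The check follows each delayed measure from the protocol tables through the SAP.

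1. **MRI.** Unscheduled scans are windowed (SAP 2.5.4, Table 5), and scans delayed past EOT by the pandemic are kept for the lesion-free endpoint (2.4.4.2.3). Retained.
2. **SDMT.** Unscheduled tests are windowed. Retained.
3. **EDSS.** There is no window, and unscheduled values are excluded from by-visit analysis, so a delayed value drops out of the 2.4.4.2.4 summary. It remains in sustained progression: 2.4.4.3.2 uses every EDSS measurement for onset and has two COVID rules that keep delayed values, one of them for confirmation only. It also reaches disease-free status, which uses 24-week progression (2.4.4.2.6).
4. **Cognitive Battery.** There is no window and no COVID rule. SAP Appendix B lists a descriptive summary and nothing else. SAP 2.4.4.2.6 mentions that cognitive information might be explored in other disease-free definitions, but defines none.

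If SDMT and battery are done at one delayed session, the SDMT is windowed and the battery is not.

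**Why the battery is most exposed.** Treatment runs to 192 weeks after randomisation. A patient who completes 96 double-blind weeks has 192 − 96 = 96 open-label weeks. Open-label Week 96 is then that patient's EOT, and the battery is done once. Patients who switch early can have two.

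**Would the SDMT windows serve for EDSS?** Target day = 7 × week + 1. On-site open-label visits are 12-weekly from Week 12, and EDSS is 24-weekly. The next on-site visit after a missed EDSS is therefore 12 × 7 = 84 days later and has no EDSS slot.

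- Week 24: 7 × 24 + 1 = 169; 169 + 84 = 253. The SDMT window ends at 252.
- Week 96: 7 × 96 + 1 = 673; 673 + 84 = 757. The SDMT window ends at 756; the MRI window ends at 840.
- With a 42-day delay, Week 96 gives 673 + 42 = 715, inside the SDMT window.

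A 12-week delay thus misses the SDMT window by one day. The value moves to the next visit's window, where a test nearer the target would displace it. Copying the SDMT windows would not solve the problem.

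**Would assignment to the replaced visit collide with the next one?** With the 7-day visit window, the latest such Week 24 EDSS is at day 169 + 84 + 7 = 260. The Week 48 visit opens at 337 − 7 = 330. There is no overlap.

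**The case against.** The strongest reply is that little is lost. SAP 2.5.4 restricts by-visit analysis only, and SAP 2.1.3 includes all efficacy evaluations unless otherwise specified. A reader might infer that delayed EDSS is discarded altogether. The documents do not support that, because progression and disease-free status keep it. This part of the reply stands in full.

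Second, section 8.1 and the memo text say *or* as unscheduled evaluation, so a test done at a scheduled visit might be filed under that visit. This stands as an ambiguity. It does not settle the matter: the tables combine the two, the next 12-weekly visit often has no EDSS or battery slot, and the SAP does not say how such a record is classified.

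Third, SAP 2.4.4.2.5 does not say the battery is summarised at each visit. Protocol 11.4.4.2 does, but for the placebo-controlled period. On a narrow reading the general inclusion rule keeps the battery. That reading is possible; the SAP should not leave it open.

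Fourth, the flow charts define EOT as the first visit after the last dose, so a wholly postponed EOT visit may still count as EOT. It would be too strong to infer that any delayed visit removes a patient's open-label cognitive outcome. The loss arises only when the later battery is logged as unscheduled.

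Finally, a reader might size the problem from dates: 24 March 2020 less 192 × 7 = 1,344 days is 19 July 2016, so a patient randomised from then had the last planned visit on or after the global memo. That marks possible exposure. It does not count delayed tests, and the documents do not show that losses cluster by country or enrolment date.

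**Conclusion.** The protocol's recording instruction and SAP 2.5.4 do not fit together for EDSS and the Cognitive Battery. For EDSS the effect is limited to the descriptive by-visit table. For the battery it reaches the only defined analysis, and for a patient with 96 open-label weeks it could reach the only open-label result.

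This rests on two assumptions: that sites enter the delayed test as unscheduled, as protocol Tables 5 and 6 direct, and that the battery summary counts as by-visit analysis. The number of patients affected is not stated. SAP 2.4.4 calls the open-label efficacy analyses exploratory, and the double-blind primary analysis is untouched. The point is modest, but cheap to settle before final database lock.

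**What to change.** Add to SAP 2.5.4 that EDSS and Cognitive Battery results recorded as unscheduled because of a declared emergency are assigned to the planned visit they replace, up to a stated maximum delay, and flagged in the summaries. The maximum should cover at least the next 12-weekly on-site visit with its window: 84 + 7 = 91 days. Assignment to the replaced visit avoids the one-day miss that the SDMT windows would cause.

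EDSS from unscheduled relapse visits stays excluded, and the handling of scheduled EDSS does not change. The 30-day limit after relapse onset in SAP 2.4.4.3.2 should not be carried over: it governs confirmation of progression only, and applied here it could remove scheduled values that are now kept.

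The cost is about two sentences and a flag. The downside is somewhat wider timing around the nominal visit, which the SAP already accepts for MRI and SDMT.

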2.5.5 Pooling of centers for statistical analyses

Study centers will be pooled into geographical regions for statistical analysis. Final adjustment to the region list will be made before the database lock.

- Europe: Belgium, Bulgaria, Estonia, France, Greece, Lithuania, Netherlands, Portugal, Russian federation, Serbia, Spain, Ukraine, United Kingdom
- North America: Canada, United States
- Asia: China
- Middle East: Turkey, Israel, Lebanon
- North Africa: Tunisia, Morocco.

2.5.6 Statistical technical issues

Not Applicable.

3 INTERIM ANALYSIS

An interim analysis for open label CSR is planned at core DBL (ie, approximately 28 days after last patient last visit in the double-blind period of this study).

Only data collected up to the date of core DBL will be used for this interim analysis. Analysis results will be summarized in an interim CSR for this open-label period.

Summary of patient disposition, demographics and key baseline characteristics, concomitant medications, extent of IMP exposure and compliance will be provided, as described in [Section 2.2](#), [Section 2.4.1](#), [Section 2.4.2](#), and [Section 2.4.3](#), respectively, in the interim analysis report.

For efficacy endpoints, the interim analysis will be performed for the following efficacy endpoints in which details are provided in [Section 2.4.4](#).

- Time to first clinical relapse after randomization up to the end the open-label treatment period
- Time to first clinical relapse after enrollment of open-label period up to the end of open-label period
- Proportion of clinical relapse-free patients
- Magnetic resonance imaging (MRI) variables
 - Number of new/newly enlarged T2 lesions
 - Number of Gd-enhancing T1 lesions
 - Change in volume of T2 lesions
 - Change in volume of T1 hypointense lesions
 - Number of new hypointense T1 lesions
 - Proportion of patients free of new or enlarged MRI T2 lesions at 48, 96, 144 and 192 weeks
 - Percentage change in brain volume
- Cognitive outcome measured by the SDMT and Cognitive Battery Tests
- Annualized relapse rate
- Sustained disability progression (using EDSS).

Summary of teriflunomide PK levels at each visit will also be provided with descriptive statistics.

For safety endpoints, key safety results including TEAE, SAE, AESI, death, AEs leading to treatment discontinuation along with related laboratory values, vital signs, and Tanner scales, in which details are provided in [Section 2.4.4.4](#) will be provided in the interim analysis report. Long-term safety data reported in the double-blind and the open-label treatment period s will also be performed for this interim CSR.

4 DATABASE LOCK

The interim database is planned to be locked approximately 28 days after last patient last visit in the double-blind period. The final database is planned to be locked approximately 28 days after last patient last visit in the open-label period of the study. This final database lock will not include patient data collected in the optional additional extension period beyond the final DBL of the study.

5 SOFTWARE DOCUMENTATION

All summaries and statistical analyses will be generated using SAS Version 9.2 or higher.

7 LIST OF APPENDICES

[Appendix A](#): Potentially clinically significant abnormalities (PCSA) criteria

[Appendix B](#): Summary of statistical analyses

[Appendix C](#): Flow chart for open label extension period

Appendix A Potentially clinically significant abnormalities criteria

Criteria for potentially clinically significant abnormalities For studies in children (Version 3.0 May 2014)			
Parameter	Age range	PCSA	Comments
ECG parameters			Ref. : Rijnbeek P.R. et al., Eur Heart J 2001; Davignon A. et al., Ped Cardiol 1979/1980; Semizel E. et al., Cardiol Young 2008; Mulberg AE et al. Pediatric Drug Development Concepts and applications. John Wiley & sons, Inc. 2009
HR	Birth/0 to 27 days old (Neonates)	≤90 bpm and decrease from baseline ≥20 bpm ≥190 bpm and increase from baseline ≥20 bpm	
	28 days/1 month to 23 months old (Infants)	≤80 bpm and decrease from baseline ≥20 bpm ≥175 bpm and increase from baseline ≥20 bpm	
	24 months/2 years to <6 years old (Children)	≤75 bpm and decrease from baseline ≥20 bpm ≥140 bpm and increase from baseline ≥20 bpm	
	6 to <12 years old (Children)	≤50 bpm and decrease from baseline ≥20 bpm ≥120 bpm and increase from baseline ≥20 bpm	
	12 to 16/18 years old (Adolescents)	≤50 bpm and decrease from baseline ≥20 bpm ≥120 bpm and increase from baseline ≥20 bpm	
PR	Birth/0 to 27 days old (Neonates)	≥120 ms	
	28 days/1 month to 23 months old (Infants)	≥140 ms	
	24 months/2 years to <6 years old (Children)	≥160 ms	
	6 to <12 years old (Children)	≥170 ms	
	12 to 16/18 years old (Adolescents)	≥180 ms	

**Criteria for potentially clinically significant abnormalities
For studies in children
(Version 3.0 May 2014)**

Parameter	Age range	PCSA	Comments
QRS	Birth/0 to 27 days old (Neonates)	≥85 ms	
	28 days/1 month to 23 months old (Infants)	≥85 ms	
	2 to <6 years old (Children)	≥95 ms	
	6 to <12 years old (Children)	≥100 ms	
	12 to 16/18 years old (Adolescents)	≥110 ms	
QTc	Birth/0 to <12 years old (Neonates, Infants, Children)	Absolute values (ms) Borderline: 431-450 ms Prolonged*: >450 ms Additional: ≥500 ms AND Increase from baseline Borderline: Increase from baseline 30-60 ms Prolonged*: Increase from baseline >60 ms	To be applied to QTcF *QTc prolonged and ΔQTc >60 ms are the PCSA to be identified in individual subjects/patients listings.
	12 to 16/18 years old (Adolescents)	Borderline: 431-450 ms (Boys); 451-470 ms (Girls) Prolonged*: >450 ms (Boys); >470 ms (Girls) Additional: ≥500 ms AND Increase from baseline Borderline: Increase from baseline 30-60 ms Prolonged*: Increase from baseline >60 ms	

**Criteria for potentially clinically significant abnormalities
For studies in children
(Version 3.0 May 2014)**

Parameter	Age range	PCSA	Comments
Vital Signs			Ref. : Kidney Disease Outcomes Quality Initiatives (KDOQI) Guideline 13; 1996; The fourth report on the diagnosis, evaluation, and treatment of high blood pressure in children and adolescents, Pediatrics 2004; Bowman E & Fraser S Neonatal Handbook 2012; Mulberg AE et al. Pediatric Drug Development Concepts and applications. John Wiley & sons, Inc. 2009; Pediatric respiratory rates http://www.health.ny.gov/
SBP	Birth/0 to 27 days old (Neonates)	≤60 mmHg and decrease from baseline ≥20 mmHg ≥85 mmHg and increase from baseline ≥20 mmHg	Based on definition of Hypertension as average SBP or DBP ≥95th percentile for gender, age, and height on ≥3 occasions
	28 days/1 month to 23 months old (Infants)	≤70 mmHg and decrease from baseline ≥20 mmHg ≥98 mmHg and increase from baseline ≥20 mmHg	
	24 months/2 years to <6 years old (Children)	≤70 mmHg and decrease from baseline ≥20 mmHg ≥101 mmHg and increase from baseline ≥20 mmHg	
	6 to <12 years old (Children)	≤80 mmHg and decrease from baseline ≥20 mmHg ≥108 mmHg and increase from baseline ≥20 mmHg	
	12 to 16/18 years old (Adolescents)	≤90 mmHg and decrease from baseline ≥20 mmHg ≥119 mmHg and increase from baseline ≥20 mmHg	
	DBP	Birth/0 to 27 days old (Neonates)	
DBP	28 days/1 month to 23 months old (Infants)	≤34 mmHg and decrease from baseline ≥10 mmHg ≥54 mmHg and increase from baseline ≥10 mmHg	
	24 months/2 years to <6 years old (Children)	≤34 mmHg and decrease from baseline ≥10 mmHg ≥59 mmHg and increase from baseline ≥10 mmHg	
	6 to <12 years old (Children)	≤48 mmHg and decrease from baseline ≥10 mmHg ≥72 mmHg and increase from baseline ≥10 mmHg	
	12 to 16/18 years old (Adolescents)	≤54 mmHg and decrease from baseline ≥10 mmHg ≥78 mmHg and increase from baseline ≥10 mmHg	

**Criteria for potentially clinically significant abnormalities
For studies in children
(Version 3.0 May 2014)**

Parameter	Age range	PCSA	Comments
Orthostatic hypotension	All age ranges	SBP: St - Su \leq -20 mmHg DBP: St - Su \leq -10 mmHg	
Temperature	All age ranges	Rectal, ear or temporal artery: \geq 100.4°F/38.0°C Oral or pacifier: \geq 99.5°F/37.5°C Axillary or skin infrared: \geq 99°F/37.2°C	Ear temperature not accurate below 6 months of age
Respiratory rate	Birth/0 to 27 days old (Neonates)	<30 per minutes >60 per minutes	Based on normal range
	28 days/1 month to 23 months old (Infants)	<24 per minutes >40 per minutes	
	24 months/2 years to <6 years old (Children)	<22 per minutes >34 per minutes	
	6 to <12 years old (Children)	<18 per minutes >30 per minutes	
	12 to 16/18 years old (Adolescents)	<12 per minutes >20 per minutes	
SaO2	All age ranges	\leq 95%	
Weight	All ranges	\geq 5% weight loss from baseline	Based on identification of trends in the child's growth with a series of visits WHO Multicentre Reference Study Group, 2006; Center for Disease Control. Growth chart 2007

**Criteria for potentially clinically significant abnormalities
For studies in children
(Version 3.0 May 2014)**

Parameter	Age range	PCSA	Comments
Clinical Chemistry			
ALT/SGPT	All age ranges	>3 ULN By distribution analysis: >3 ULN >5 ULN >10 ULN >20 ULN	Ref Molleston JP et al. JPGN 2011; Moritz et al., Pediatrics 1999; Moritz et al., Pediatr Nephrol 2005 ; Sedlacek et al., Seminars in Dialysis 2006) Gong G et al. Clinical Biochemistry 2009; Masilamani et al. Arch Dis Children 2012; Mulberg AE et al. Pediatric Drug Development Concepts and applications. John Wiley & sons, Inc. 2009 Based on normal ranges: 6 to 50 U/L (0-5 days), 5 to 45 U/L (1-19 years)
AST/SGOT	All age ranges	>3 ULN By distribution analysis: >3 ULN >5 ULN >10 ULN >20 ULN	Based on normal ranges: 35 to 140 U/L (0-5 days), 15 to 55 U/L (1-9 years), 5 to 45 U/L (10-19 years)
Alkaline Phosphatase	All age ranges	≥1.5 ULN	Based on normal ranges: 145 to 420 U/L (1-9 years), 130 to 560 U/L (10-11 years), 200 to 495 U/L (Boys 12-13 years), 105 to 420 U/L (Girls 12-13 years), 130 to 525 U/L (Boys 14-15 years), 70 to 130 U/L (Girls 14-15 years), 65 to 260 U/L (Boys 16-19 years), 50 to 130 U/L (Girls 16-19 years)
Total Bilirubin	All age ranges	≥1.3 ULN	CF = mg x 1.7 = μmol Based on normal ranges: <6 mg/dL (Term 0-1 day), <8 mg/dL (Term 1-2 days), <12 mg/dL (Term 3-5 days), <1 mg/dL (Term >5 days)
Conjugated Bilirubin	All age ranges	>35% Total Bilirubin and TBILI≥1.3 ULN	CF = mg x 1.7 = μmol Based on normal range: 0 to 0.4 mg/dL

**Criteria for potentially clinically significant abnormalities
For studies in children
(Version 3.0 May 2014)**

Parameter	Age range	PCSA	Comments
ALT and Total Bilirubin	All age ranges	ALT ≥3 ULN and Total Bilirubin ≥2 ULN	
CPK	All age ranges	≥3 ULN	
Creatinine	Birth/0 to <6 years old (Neonates, Infants, Children)	>53 µmol/L or 0.6 mg/dL	CF = mg x 8.8 = µmol Based on normal ranges: <0.6 mg/dL (0-1 year), 0.5 to 1.5 mg/dL (1 to 16/18 years)
	6 years to <12 years old (Children)	>90 µmol/L or 1.1mg/dL	
	12 years to 16/18 years old (Adolescents)	>132 µmol/L or 1.5mg/dL	
Creatinine Clearance	All age ranges	50 % of normal <60 mL/min/1.73m ² (After 1 year old)	Based on GFR Bedside Schwartz Formula Based on normal ranges: 20 to 50 (<8 days), 25 to 80 (8 days to 1 month), 30 to 90 (1-6 months), 40 to 115 (6-12 months), 60 to 190 (12-23 months), 90 to 165 (2-12 years), 80-120 (After 12 years)
Uric Acid	All age ranges	<2.0 mg/dL or 119 µmol/L >8.0 mg/dL or 476 µmol/L	CF = mg x 5.95 = µmol Based on normal ranges: 2.4 to 6.4 mg/dL
Blood Urea Nitrogen (BUN)	Birth/0 to 27 days old (Neonates)	≥4.3 mmol/L or 12 mg/dL	CF = g x 16.66 = mmol Based on normal ranges: 3 to 12 mg/dL (NN; 5 to 18 mg/dL (other classes of age)
	28 days/1 month to 16/18 years old (Infants, Children, Adolescents)	≥6.4 mmol/L or 18 mg/dL	
Chloride	All age ranges	≤80 mmol/L or 80 mEq/L ≥115 mmol/L or 115 mEq/L	CF = 1 Based on normal range: 98 to 106
Sodium	All age ranges	≤129 mmol/L or 129 mEq/L ≥150 mmol/L or 150 mEq/L	CF = 1 Based on normal range : 134 to 146
Potassium	Birth/0 to 27 days old (Neonates)	≤3.0 mmol/L or 3.0 mEq/L ≥7.0 mmol/L or 7.0 mEq/L	CF = 1 Based on normal ranges: 3.0 to 7.0 (NN); 3.5 to 6.0 (Infants); 3.5 to 5.0 (>Infants)
	28 days/1 month to 23 months old (Infants)	≤3.5 mmol/L or 3.5 mEq/L ≥6.0 mmol/L or 6.0 mEq/L	
	24 months/2 years to 16/18 years old (Children, Adolescents)	≤3.5 mmol/L or 3.5 mEq/L ≥5.5 mmol/L or 5.5 mEq/L	
Bicarbonate	All age ranges	≤16 mmol/L or 16 mEq/L ≥30 mmol/L or 30 mEq/L	CF = 1 Based on normal range: 18 to 26

**Criteria for potentially clinically significant abnormalities
For studies in children
(Version 3.0 May 2014)**

Parameter	Age range	PCSA	Comments
Calcium total	All age ranges	≤2.0 mmol/L or 8.0 mg/dL ≥2.9 mmol/L or 11.6 mg/dL	CF = mg x 0.025 = mmol Based on normal range: 8.4 to 10.9 mg/dL
Calcium ionized	All age ranges	≤1.0 mmol/L or 4.0 mg/dL ≥1.4 mmol/L or 5.6 mg/dL	CF = mg x 0.025 = mmol Based on normal range: 4.0 to 5.1 mg/dL
Total Cholesterol	All age ranges	>6.20 mmol/L or 240 mg/dL	CF = g x 2.58 = mmol Based on normal ranges: 45 to 182 mg/dL (1-3 years), 109 to 189 mg/dL (4-6 years), 126 to 191 mg/dL (Boys 6-9 years), 122 to 209 mg/dL (Girls 6-9 years), 130 to 204 mg/dL (Boys 10-14 years), 124-217 mg/dL (Girls 10-14 years), 114 to 198 mg/dL (Boys 15-19 years), 125 to 212 mg/dL (Girls 14-19 years)
Triglycerides	All age ranges	>4.0 mmol/L or 350 mg/dL	After >12 hours of fast) CF = g x 1.14 = mmol Based on normal ranges: 30 to 86 mg/dL (Boys 0-5 years), 32 to 99 mg/dL (Girls 0-5 years), 31-108 mg/dL (Boys 6-11 years), 35 to 114 mg/dL (Girls 6-11 years), 36 to 138 mg/dL (Boys 12-15 years), 43 to 138 mg/dL (Girls 12-15 years), 40 to 163 mg/dL (Boys 16-19 years), 40-128 mg/dL (Girls 16-19 years)
Lipasemia	All age ranges	>2 ULN	Based on normal ranges: 3 to 32 U/L (1-18 years)
Amylasemia	All age ranges	>2 ULN	Based on normal ranges: 10 to 30 U/L (NN), 10 to 45 U/L (1-18 years)
Glucose	All age ranges	Hypoglycaemia <2.7 mmol/L or 50 mg/dL Hyperglycaemia >7 mmol/L or 120 mg/dL (fasted after >12 hours of fast); >10.0 mmol/L or 180 mg/dL (unfasted)	CF = g x 5.55 = mmol Based on normal ranges: 50 to 90 mg/dL (NN), 60 to 100 mg/dL (Child)
CRP	All age ranges	>2 ULN or >10 mg/L (if ULN not provided)	Based on normal ranges: <6 mg/L

**Criteria for potentially clinically significant abnormalities
For studies in children
(Version 3.0 May 2014)**

Parameter	Age range	PCSA	Comments
Hematology			Common Terminology Criteria for Adverse Events v3.0 (CTCAE), 2006 ; Division of Microbiology and Infectious Diseases Pediatric Toxicity Tables, 2007 ; Division of AIDS Table for Grading the Severity of Adult and Pediatric Adverse Events, 2004; Mulberg AE et al. Pediatric Drug Development Concepts and applications. John Wiley & sons, Inc. 2009; Family Practice Notebook, LLC, 2012; Tietz NW et al. Clinical Guide to Laboratory Testing, 3 rd edition 1995
WBC	Birth/0 to 27 days old (Neonates)	<4.0 GIGA/L or 4000/mm ³ >25.0 GIGA/L or 25 000/mm ³	To be used if no differential count available Based on normal ranges: 9000 to 30 000/mm ³ (birth), 9400 to 38 000/mm ³ (0-1 day), 5000 to 21 000/mm ³ (1 day-1 month), 6000 to 17 500/mm ³ (1 month-2 years), 5000 to 17 000/mm ³ (2-6 years), 4500 to 15 500/mm ³ (6-11 years), 4500 to 13 500/mm ³ (11-18 years)
	28 days/1 month to 23 months old (Infants)	<4.0 GIGA/L or 4000/mm ³ >20.0 GIGA/L or 20 000/mm ³	
	24 months/2 years to <6 years old (Children)	<3.0 GIGA/L or 3000/mm ³ >16.0 GIGA/L or 16 000 /mm ³	
	6 to <12 years old (Children)	<5.0 GIGA/L or 5000/mm ³ >17.0 GIGA/L or 17 000 /mm ³	
	12 to 16/18 years old (Adolescents)	<4,5 GIGA/L or 5000/mm ³ >13.5 GIGA/L or 17 000/mm ³	
Lymphocytes (ALC)	Birth/0 to 27 days old (Neonates)	<1.2 GIGA/L or 1200/mm ³ >17.0 GIGA/L or 17 000/mm ³	Based on normal ranges: 2000 to 11 500/mm ³ (0-1 days), 2000 to 17 000/mm ³ (2 days-1 month), 3000 to 13 500/mm ³ (1 month-2 years), 1500 to 9 500/mm ³ (2-6 years), 1500 to 8000/mm ³ (6-10 years), 1200 to 5200/mm ³ (10-18 years)
	28 days/1 month to 23 months old (Infants)	<2.0 GIGA/L or 2000/mm ³ >13.5 GIGA/L or 13 500/mm ³	
	24 months/2 years to <6 years old (Children)	<1.0 GIGA/L or 1000/mm ³ >9.5 GIGA/L or 9500/mm ³	
	6 to <12 years old (Children)	<1.0 GIGA/L or 1000/mm ³ >8.0 GIGA/L or 8000/mm ³	

**Criteria for potentially clinically significant abnormalities
For studies in children
(Version 3.0 May 2014)**

Parameter	Age range	PCSA	Comments
	12 to 16/18 years old (Adolescents)	<0.6 GIGA/L or 600 /mm ³ >6.0 GIGA/L or 6000/mm ³	
Absolute Neutrophil Count (ANC)	Birth/0 to 27 days old (Neonates)	<4.0 GIGA/L or 4000/mm ³ (1 day old) <1.5 GIGA/L or 1500/mm ³ (2-7 days old) <1.25 GIGA/L or 1250/mm ³ (>7 day-1 month old) >1 ULN	Based on normal ranges: 5000 to 28 000/mm ³ (0-1 day), 1000 to 10 000 (1 day-1 month), 1000 to 8500 (1-12 months), 1500 to 8500 (1 to 6 years), 1500 to 8000 (6 to 10 years), 1800 to 8000 (10 to 18 years)
	28 days/1 month to 23 months old (Infants)	<1.0 GIGA/L or 1000/mm ³ (1-3 months) <1.2 GIGA/L or 1200/mm ³ (3-24 months) >1 ULN	
	24 months/2 years to <6 years old (Children)	<1.2 GIGA/L or 1200/mm ³ >1 ULN	
	6 to <12 years old (Children)	<1.2 GIGA/L or 1200/mm ³ >1 ULN	
	12 to 16/18 years old (Adolescents)	<1.2 GIGA/L or 1200/mm ³ >1 ULN	
Eosinophils	All age ranges	>0.5 GIGA/L or 500/mm ³ Or >ULN if ULN >0.5 GIGA/L or 500/mm ³	Based on normal ranges: 0 to 500/mm ³ (0-1 month), 0 to 300/mm ³ (1 month-18 years)
Hemoglobin	Birth/0 to 27 days old (Neonates)	< 86 mmol/L or 12.0 g/dL or any decrease >0.31 mmol/L or 2 g/dL	CF = g x 1.55 = mmol Based on normal ranges: 15 to 20 g/dL (0-3 days), 12.5 to 18.5 g/dL (1-2 weeks), 10.0 to 13.0 g/dL (1-6 months), 10.5 to 13.0 g/dL (7 months-2 years), 11.5 to 13.0 g/dL (2-5 years), 11.5 to 14.5 (5-8 years), 12.0 to 15.2 g/dL (13-18 years)
	28 days/1 month to 23 months old (Infants)	<1.40 mmol/L or 9.0 g/dL or any decrease >0.31 mmol/L or 2 g/dL	
	24 months/2 years to <16/18 years old (Children, Adolescents)	<1.55 mmol/L or 10.0 g/dL or any decrease >0.31 mmol/L or 2 g/dL	

**Criteria for potentially clinically significant abnormalities
For studies in children
(Version 3.0 May 2014)**

Parameter	Age range	PCSA	Comments
Hematocrit	Birth/0 to 27 days old (Neonates)	<0.39 l/l or 40% >0.61 l/l or 47%	CF = % x 0.01 = l/l Based on normal ranges: 45% to 61% (0-3 days), 39% to 57% (1-2 weeks), 29% to 42% (1-6 months), 33% to 38% (7 months-2 years), 34% to 39% (2-5 years), 35% to 42% (5-8 years); 36% to 47% (13-18 years)
	28 days/1 month to 23 months old (Infants)	<0.29 l/l or 29% >0.42 l/l or 42%	
	24 months/2 years to <16/18 years old (Adolescents)	<0.32 l/l or 32% >0.47 l/l or 47%	
Platelets	All age ranges	<100 GIGA/L or 100 000/mm ³ >700 GIGA/L or 700 000/mm ³	Based on normal ranges: 250 000 to 450 000/mm ³ (NN); 300 000 to 700 000/mm ³ (1-6 months), 250 000 to 600 000/mm ³ (7 months-2 years), 250 000 to 550 000/mm ³ (2-12 years), 150 000 to 450 000/mm ³ (13-18 years)
Urinalysis			Patel HP, Pediatr Clin N Am, 2006
Ketonuria	All age ranges	Presence	Semi-quantitative methods
Glycosuria	All age ranges	Presence	Semi-quantitative methods
Hematuria	All age ranges	>1+	Semi-quantitative methods
Proteinuria	All age ranges	>1+	Semi-quantitative methods

**Criteria for potentially clinically significant abnormalities
for Phase 2/3 studies (oncology excepted)
(Version 3.0 May 2014)**

Parameter	PCSA	Comments
Clinical Chemistry		
ALT	By distribution analysis : >3 ULN >5 ULN >10 ULN >20 ULN	Enzymes activities must be expressed in ULN, not in IU/L. Concept paper on DILI - FDA draft Guidance Oct 2007. Internal DILI WG Oct 2008. Categories are cumulative. First row is mandatory. Rows following one mentioning zero can be deleted.
AST	By distribution analysis : >3 ULN >5 ULN >10 ULN >20 ULN	Enzymes activities must be expressed in ULN, not in IU/L. Concept paper on DILI - FDA draft Guidance Oct 2007. Internal DILI WG Oct 2008. Categories are cumulative. First row is mandatory. Rows following one mentioning zero can be deleted.
Alkaline Phosphatase	>1.5 ULN	Enzymes activities must be expressed in ULN, not in IU/L. Concept paper on DILI - FDA draft Guidance Oct 2007. Internal DILI WG Oct 2008.
Total Bilirubin	>1.5 ULN >2 ULN	Must be expressed in ULN, not in µmol/L or mg/L. Categories are cumulative. Concept paper on DILI - FDA draft Guidance Oct 2007. Internal DILI WG Oct 2008.
Conjugated Bilirubin	>35% Total Bilirubin and TBILI>1.5 ULN	Conjugated bilirubin dosed on a case-by-case basis.
ALT and Total Bilirubin	ALT>3 ULN and TBILI>2 ULN	Concept paper on DILI – FDA draft Guidance Oct 2007. Internal DILI WG Oct 2008. To be counted within a same treatment phase, whatever the interval between measurements.

**Criteria for potentially clinically significant abnormalities
for Phase 2/3 studies (oncology excepted)
(Version 3.0 May 2014)**

Parameter	PCSA	Comments
CPK	>3 ULN >10 ULN	FDA Feb 2005. Am J Cardiol April 2006. Categories are cumulative. First row is mandatory. Rows following one mentioning zero can be deleted.
CrCl (mL/min) (Estimated creatinine clearance based on the Cockcroft-Gault equation)	<15 (end stage renal disease) ≥15 - <30 (severe decrease in GFR) ≥30 - <60 (moderate decrease in GFR) ≥60 - <90 (mild decrease in GFR) ≥ 90 (normal GFR)	FDA draft Guidance 2010 Pharmacokinetics in patients with impaired renal function-study design, data analysis, and impact on dosing and labeling
eGFR (mL/min/1.73m ²) (Estimate of GFR based on an MDRD equation)	<15 (end stage renal disease) ≥15 - <30 (severe decrease in GFR) ≥30 - <60 (moderate decrease in GFR) ≥60 - <90 (mild decrease in GFR) ≥90 (normal GFR)	FDA draft Guidance 2010 Pharmacokinetics in patients with impaired renal function-study design, data analysis, and impact on dosing and labeling
Creatinine	≥150 µmol/L (Adults) ≥30% change from baseline ≥100% change from baseline	Benichou C., 1994.
Uric Acid Hyperuricemia Hypouricemia	>408 µmol/L <120 µmol/L	Harrison- Principles of internal Medicine 17th Ed., 2008.
Blood Urea Nitrogen	≥17 mmol/L	

**Criteria for potentially clinically significant abnormalities
for Phase 2/3 studies (oncology excepted)
(Version 3.0 May 2014)**

Parameter	PCSA	Comments
Chloride	<80 mmol/L >115 mmol/L	
Sodium	≤129 mmol/L ≥160 mmol/L	
Potassium	<3 mmol/L ≥5.5 mmol/L	FDA Feb 2005.
Total Cholesterol	≥7.74 mmol/L	Threshold for therapeutic intervention.
Triglycerides	≥4.6 mmol/L	Threshold for therapeutic intervention.
Lipasemia	≥3 ULN	
Amylasemia	≥3 ULN	
Glucose		
Hypoglycaemia	≤3.9 mmol/L and <LLN	ADA May 2005.
Hyperglycaemia	≥11.1 mmol/L (unfasted); ≥7 mmol/L (fasted)	ADA Jan 2008.
HbA1c	>8%	
Albumin	≤25 g/L	
CRP	>2 ULN or >10 mg/L (if ULN not provided)	FDA Sept 2005.
Hematology		
WBC	<3.0 GIGA/L (Non-Black); <2.0 GIGA/L (Black) ≥16.0 GIGA/L	Increase in WBC: not relevant. To be interpreted only if no differential count available.
Lymphocytes	>4.0 GIGA/L	

**Criteria for potentially clinically significant abnormalities
for Phase 2/3 studies (oncology excepted)
(Version 3.0 May 2014)**

Parameter	PCSA	Comments
Neutrophils	<1.5 GIGA/L (Non-Black); <1.0 GIGA/L (Black)	International Consensus meeting on drug-induced blood cytopenias, 1991. FDA criteria.
Monocytes	>0.7 GIGA/L	
Basophils	>0.1 GIGA/L	
Eosinophils	>0.5 GIGA/L or >ULN (if ULN ≥ 0.5 GIGA/L)	Harrison- Principles of internal Medicine 17th Ed., 2008.
Hemoglobin	≤115 g/L (Male); ≤95 g/L (Female) ≥185 g/L (Male); ≥165 g/L (Female) Decrease from Baseline ≥20 g/L	Criteria based upon decrease from baseline are more relevant than based on absolute value. Other categories for decrease from baseline can be used (≥30 g/L, ≥40 g/L, ≥50 g/L).
Hematocrit	≤0.37 v/v (Male) ; ≤0.32 v/v (Female) ≥0.55 v/v (Male) ; ≥0.5 v/v (Female)	
RBC	≥6 Tera/L	Unless specifically required for particular drug development, the analysis is redundant with that of Hb. Otherwise, consider FDA criteria.
Platelets	<100 GIGA/L ≥700 GIGA/L	International Consensus meeting on drug-induced blood cytopenias, 1991.
Urinalysis		
pH	≤4.6 ≥8	
Vital signs		
HR	≤50 bpm and decrease from baseline ≥20 bpm ≥120 bpm and increase from baseline ≥20 bpm	To be applied for all positions (including missing) except STANDING.

**Criteria for potentially clinically significant abnormalities
for Phase 2/3 studies (oncology excepted)
(Version 3.0 May 2014)**

Parameter	PCSA	Comments
SBP	≤95 mmHg and decrease from baseline ≥20mmHg ≥160 mmHg and increase from baseline ≥20 mmHg	To be applied for all positions (including missing) except STANDING.
DBP	≤45 mmHg and decrease from baseline ≥10 mmHg ≥110 mmHg and increase from baseline ≥10 mmHg	To be applied for all positions (including missing) except STANDING.
Orthostatic Hypotension		
Orthostatic SDB		
Orthostatic DBP	≤-20 mmHg ≤-10 mmHg	
Weight	≥5% increase from baseline ≥5% decrease from baseline	FDA Feb 2007.
ECG		Ref.: ICH E14 guidance (2005) and E14 Q&A (2012), and Cardiac Safety Research Consortium White Paper on PR and QRS (Nada et al. Am Heart J. 2013; 165(4) : 489-500)
HR	<50 bpm <50 bpm and decrease from baseline ≥20 bpm <40 bpm <40 bpm and decrease from baseline ≥20 bpm <30 bpm <30 bpm and decrease from baseline ≥20 bpm >90 bpm >90 bpm and increase from baseline ≥20bpm >100 bpm >100 bpm and increase from baseline ≥20bpm >120 bpm >120 bpm and increase from baseline ≥20 bpm	Categories are cumulative Categories are cumulative

**Criteria for potentially clinically significant abnormalities
for Phase 2/3 studies (oncology excepted)
(Version 3.0 May 2014)**

Parameter	PCSA	Comments
PR	>200 ms >200 ms and increase from baseline \geq 25% > 220 ms >220 ms and increase from baseline \geq 25% > 240 ms > 240 ms and increase from baseline \geq 25%	Categories are cumulative
QRS	>110 ms >110 ms and increase from baseline \geq 25% >120 ms >120 ms and increase from baseline \geq 25%	Categories are cumulative
QT	>500 ms	
QTc	Absolute values (ms) >450 ms >480 ms >500 ms Increase from baseline Increase from baseline]30-60] ms Increase from baseline >60 ms	To be applied to any kind of QT correction formula. Absolute values categories are cumulative QTc >480 ms and Δ QTc>60 ms are the 2 PCSA categories to be identified in individual subjects/patients listings.

